4.3. Sample Size and Power

Part A.1

With approximately 300 and 584 participants exposed to 50 and 100 µg of mRNA-1273.211, respectively, there is at least 90% probability to observe one participant at each dose level reporting an AE if the true rate of AEs is 1%.

Part A.2

We anticipate approximately 300 participants will be enrolled in Part A.2, there is no statistical hypothesis testing in Part A.2.

Part B

With approximately 300 participants exposed to 100 µg of mRNA-1273, there is at least 90% probability to observe one participant reporting an AE if the true rate of AEs is 1%.

Part C

With approximately 584 participants exposed to each dose of mRNA-1273.617.2, there is at least 90% probability in each group to observe one participant reporting an AE if the true rate of AEs is 1%.

Part D

With approximately 584 participants exposed to each dose of mRNA-1273.213, there is at least 90% probability to observe one participant reporting an AE if the true rate of AEs is 1%.

Part E

The target enrollment of the mRNA-1273.213 in this part of the study is between 50 and 100 participants, with a subset of enrolled participants who previously received Moderna's mRNA-1273 authorized vaccine as a primary series. The sample size for Part E is not driven by statistical assumptions for hypothesis testing.

Part F

mRNA-1273.529 in each cohort will be assessed at a 2-sided type I error rate of 5%.

Cohort 1:

The target enrollment is approximately 375 participants for 50 µg mRNA-1273.529. Assuming 20% of participants will be excluded from the Per-Protocol Immunogenicity SARS-CoV-2 Negative Set (PPIS-Neg), with approximately 300 participants in 50 µg mRNA-1273.529 and 300 participants in 50 µg mRNA-1273 (external comparator, see [Section 4.6](#)) in the PPIS-Neg, there is approximately 89% global power for the primary immunogenicity objectives with alpha level of 0.05 (2-sided). The assumptions are: the true GMR (mRNA-1273.529 booster vs. 50 µg mRNA-1273 booster) against the variant (B.1.1.529) is 1.5, the standard deviation of the log-transformed titer is 1.5, and the non-inferiority margin for GMR is 1.5; the true SRR against B.1.1.529 after a single booster dose of 50 µg mRNA-1273.529 is 90% (same assumption for 50 µg mRNA-1273), and non-inferiority margin for SRR difference is 10%.

With approximately 375 participants exposed to 50 µg mRNA-1273.529, there is at least 90% probability in this group to observe 1 participant reporting an AE if the true rate of AEs is 1%.

Cohort 2:

The target enrollment is approximately 750 participants for 50 µg mRNA-1273.529 and 50 µg mRNA-1273 (1:1 ratio). Assuming 20% of participants will be excluded from the PPIS-Neg, with approximately 300 participants each in 50 µg mRNA-1273.529 and 50 µg mRNA-1273 in the Per-Protocol Immunogenicity Set (PPIS) and SARS-CoV-2 negative, there is approximately 89% global power to demonstrate the primary immunogenicity objectives of alpha level of 0.05 (2-sided). The assumptions are: the true GMR (mRNA-1273.529 as the second booster vs 50 µg mRNA-1273 as the second booster) against the variant (B.1.1.529) is 1.5, the standard deviation of the log-transformed titer is 1.5, and the non-inferiority margin for GMR is 1.5; the true SRR against B.1.1.529 after 50 µg mRNA-1273.529 as a second booster dose is 90% (same assumption for 50 µg mRNA-1273), and non-inferiority margin for SRR difference is 10%.

With approximately 375 participants exposed to each group, there is at least 90% probability in each group to observe 1 participant reporting an AE if the true rate of AEs is 1%.

Part G

The target enrollment is approximately 375 participants for 50 µg mRNA1273.214. Hypotheses testing will be performed at Day 29 and Day 91, alpha of 0.025 (2-sided) will be allocated equally to each one of the two time points. Assuming 20% of participants will be excluded from the PPIS-Neg, with approximately 300 participants in 50 µg mRNA1273.214 and 300 participants in 50 µg mRNA-1273 (Part F, Cohort 2-50 µg mRNA-1273) in the PPIS and SARS-CoV-2 negative, there is approximately 71% global power to demonstrate the primary immunogenicity objectives with alpha of 0.025 (2-sided) at each time point. The assumptions are: the true GMR (mRNA-1273.214 second booster vs. 50 µg mRNA-1273 second booster) against the variant (B.1.1.529) is 1.5, the true GMR against ancestral SARS-CoV-2 is 1, the standard deviation of the log-transformed titer is 1.5, and the non-inferiority margin for GMR is 1.5, the true SRR against B.1.1.529 after mRNA-1273.214 as a second booster dose is 90% (same assumption for both 50 µg

mRNA-1273.214 and 50 μ g mRNA-1273), and non-inferiority margin for SRR difference is 10%.

With approximately 375 participants exposed to 50 μ g mRNA-1273.214, there is at least 90% probability in this group to observe 1 participant reporting an AE if the true rate of AEs is 1%.

Part H

The target enrollment is approximately 500 participants for 50 μ g mRNA1273.222. Assuming 40% of participants will be excluded from the PPIS-Neg (due to a SARS-CoV-2 infection pre-booster), with approximately 300 participants in 50 μ g mRNA1273.222 and 260 participants in 50 μ g mRNA-1273 (Part F, Cohort 2-50 μ g mRNA-1273) in the PPIS and SARS-CoV-2 negative, there is approximately 60% power to demonstrate the primary immunogenicity objectives with alpha of 0.05 (2-sided) at Day 29. The assumptions are: the true GMR (mRNA-1273.222 second booster vs. 50 μ g mRNA-1273 second booster) against Omicron BA.4/5 is 1.5, GMR (mRNA-1273.222 second booster vs. mRNA-1273 second booster) against ancestral SARS-CoV-2 D614G is 1, the standard deviation of the log-transformed titer is 1.5, and the non-inferiority margin for GMR is 1.5. The true SRR against Omicron BA.4/5 after mRNA-1273.222 as a second booster dose is 95% (same assumption for 50 μ g mRNA-1273), and non-inferiority margin for SRR difference against Omicron BA.4/5 is 5%. The true SRR against ancestral SARS-CoV-2 D614G after mRNA-1273.222 as a second booster dose is 95% (same assumption for 50 μ g mRNA-1273), and the non-inferiority margin for SRR difference against ancestral SARS-CoV-2 D614G is 10%.

With approximately 500 participants exposed to 50 μ g mRNA-1273.222, there is at least 90% probability in this group to observe 1 participant reporting an AE if the true rate of AEs is 1%.

Part J

The sample size for Part J is not driven by statistical assumptions for formal hypothesis testing. The number of proposed participants is considered sufficient to provide a descriptive summary of the safety and immunogenicity of each treatment arm.

The target enrollment is approximately 100 participants who will be randomized in a 1:1 ratio to receive either mRNA-1273.815 (50 μ g) or mRNA-1273.231 (50 μ g).

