2.1. Primary Objectives

This study consists of 9 parts: A (1, 2), B, C, D, E, F, G, H and J. The primary objectives for each study part are the following:

Part A.1

50 µg mRNA-1273.211 and 100 µg mRNA-1273.211:

- To evaluate the safety and reactogenicity of mRNA-1273.211.

Part A.2

Second booster dose 50 µg mRNA-1273.214 for participants who received mRNA-1273.211 50 µg as a first booster dose in Part A.1:

- To evaluate the immunogenicity of mRNA-1273.214 (50 µg) as a second booster dose in participants who previously received a first booster dose of mRNA-1273.211 (50 µg).
- To assess the safety and reactogenicity of the mRNA-1273.214 (50 µg) given as a second booster dose in participants who previously received a first booster dose of mRNA-1273.211 (50 µg).

Part B

100 µg mRNA-1273:

- To evaluate the safety and reactogenicity of mRNA-1273.

Part C

50 µg mRNA-1273.617.2 and 100 µg mRNA-1273.617.2:

- To evaluate the safety and reactogenicity of mRNA-1273.617.2.

Part D

50 µg of mRNA-1273.213 and 100 µg mRNA-1273.213:

- To evaluate the safety and reactogenicity of mRNA-1273.213.

Part E

100 µg mRNA-1273.213:

- To evaluate the safety and reactogenicity of mRNA-1273.213.

Part F (Cohort 1)

50 µg mRNA-1273.529 for participants who previously received 100 µg primary series and have not received a mRNA-1273 booster dose previously:

- To demonstrate non-inferiority of the antibody response against the Omicron variant (B.1.1.529) of a first booster dose of mRNA-1273.529 compared to a first booster dose of mRNA-1273 (50 µg) based on GMT ratio and SRR difference.
- To demonstrate superiority of the antibody response against the Omicron variant (B.1.1.529) of a first booster dose of mRNA-1273.529 compared to a first booster dose of mRNA-1273 (50 µg) based on GMT ratio.
- To evaluate the safety and reactogenicity of mRNA-1273.529.

Part F (Cohort 2)

Second booster dose of 50 µg mRNA-1273.529 or 50 µg mRNA-1273 for participants who previously received 100 µg primary series and a booster dose of 50 µg mRNA-1273:

- To demonstrate non-inferiority of the antibody response against the Omicron variant (B.1.1.529) of a second booster dose of mRNA-1273.529 compared to a second booster dose of mRNA-1273 (50 µg) based on GMT ratio and SRR difference.
- To demonstrate superiority of the antibody response against the Omicron variant (B.1.1.529) of a second booster dose of mRNA-1273.529 compared to a second booster dose of mRNA-1273 (50 µg) based on GMT ratio.

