4.2. Statistical Hypotheses

Parts A.1, A.2, B, C, and D

There is no hypothesis testing for Parts A.1, A.2, B, C, and D.

Part E

There will be no formal hypothesis testing for Part E. All analyses will be descriptive.

Part F (Cohort 1)

50 µg mRNA-1273.529 as a first booster dose will be assessed with respect to mRNA-1273 as a first booster dose using mRNA-1273-P201 part B 50 µg booster after 100 µg primary series as an external comparator.

For the primary objective on immune response, hypotheses are:

- 50 µg mRNA-1273.529, as a single booster dose, against the variant B.1.1.529 is either non-inferior or superior to the booster dose of (50 µg) mRNA-1273 against B.1.1.529 based on the GMT ratio of mRNA-1273.529 against the variant B.1.1.529 at Day 29 compared to mRNA-1273 against the variant B.1.1.529 at Day 29 with a non-inferiority margin of 1.5.
- 50 µg mRNA-1273.529, as a single booster dose, against the variant B.1.1.529 is non-inferior to the booster dose of (50 µg) mRNA-1273 against B.1.1.529 based on the difference in SRR at Day 29 with a non-inferiority margin of 10%.

The primary immunogenicity objective is considered met if non-inferiority against B.1.1.529 (based on GMR and SRR difference) is demonstrated.

Part F (Cohort 2)

50 µg mRNA-1273.529 as a second booster dose will be compared to 50 µg mRNA-1273 as a second booster dose.

For the primary objective on immune response, hypotheses are:

- 50 µg mRNA-1273.529, as a second booster dose, against the variant B.1.1.529 is either non-inferior or superior to the second booster dose of (50 µg) mRNA-1273 against B.1.1.529 based on the GMT ratio of mRNA-1273.529 against the variant B.1.1.529 at Day 29 compared to mRNA-1273 against the variant B.1.1.529 at Day 29 with a non-inferiority margin of 1.5.

- 50 µg mRNA-1273.529, as a second booster dose, against the variant B.1.1.529 is non-inferior to the booster dose of (50 µg) mRNA-1273 against B.1.1.529 based on the difference in SRR at Day 29 with a non-inferiority margin of 10%.

The primary immunogenicity objective is considered met if non-inferiority against B.1.1.529 (based on GMR and SRR difference) is demonstrated.

[figure not shown]
Part G

50 µg mRNA-1273.214 as a second booster dose will be compared to 50 µg mRNA-1273 as the second booster dose (active control arm in Part F, Cohort 2, booster-to-booster comparison for the 2nd booster).

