4.5. Blinding and Unblinding

Not applicable.

4.6. External Comparator for Part F Cohort 1 - Study mRNA-1273-P201 Part B Subjects

Study mRNA-1273-P201 (P201) Part B, is the Open-Label Interventional Phase of the study, and was prompted by the authorization of a COVID-19 vaccine under an EUA. In Part B, all participants who previously received 1 or 2 injections of mRNA-1273 (50 µg or 100 µg) vaccine were able to receive a single booster dose of mRNA-1273 (50 µg). A total of approximately 150 participants in the P201 50 µg mRNA-1273 booster arm who were primed with 2 doses of 100 µg mRNA-1273 will serve as an external comparator for the P205 Part F 50 µg mRNA-1273.529 arm (Cohort 1).

5. Analysis Sets

The following analysis sets are defined: All Enrolled Set, Full Analysis Set, Per-Protocol Immunogenicity Set, Per-Protocol Immunogenicity Sensitivity Set, Per-Protocol Immunogenicity SARS-CoV-2 Negative Set, Solicited Safety Set, Safety Set, and Per-Protocol Efficacy Set. Definitions are the same across study Parts A (1, 2), B, C, D, E, F, G, H and J when applicable.

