6.4.3. Primary Analysis of Antibody-Mediated Immunogenicity Endpoints

Part A.2

For Part A.2 participants, Day 29 and Day 181 immune response after mRNA-1273.214 (50 µg) as a second booster dose will be compared with their own Day 29 and Day 181 immune response of mRNA-1273.211 (50 µg) received as the first booster dose. GMT ratios will be calculated by back transforming the mean of paired differences of antibody titer data on the logarithmic scale between Day 29 and Day 181 post mRNA-1273.214 and Day 29 and Day 181 of antibody titer data post mRNA-1273.211. CIs for the GMT ratio will be based on t-distribution of the log-transformed values then back transformed to the original scale for presentation. Seroresponse rates at Day 29 and Day 181 post mRNA-1273.214 will be compared with their seroresponse rates at Day 29 and Day 181 post

mRNA-1273.211. The difference in seroresponse rates and its corresponding 95% CI based on adjusted Wald method will be provided.

Part F Cohort 1

Primary analysis set for immunogenicity objectives will be based on PPIS-Neg.

For the primary objective on immune response for a first booster dose of 50 μ g mRNA-1273.529, see [Section 4.2](#). An analysis of covariance (ANCOVA) model will be performed to assess the difference in immune response between mRNA-1273.529 and mRNA-1273 (P201B 50 μ g booster after 100 μ g primary series) as the first booster dose. For immune response against the B.1.1.529 strain, in the ANCOVA model, antibody titers at Day 29 post-booster against the B.1.1.529 strain will be a dependent variable, and a group variable (mRNA-1273.529 and mRNA-1273) will be the fixed effect, adjusting for age groups (< 65 , ≥ 65 years) and pre-booster antibody titer level if applicable; the model may also be adjusted for other characteristics.

The GMT will be estimated by the GLSM from the model and its corresponding 95% will be provided for each group. The GMR (ratio of GMTs) for mRNA-1273.529 with respect to mRNA-1273 will be estimated by the ratio of GLSM from the model and the corresponding 95% CIs will be provided. The 95% CI for GMR will be used to assess the between group difference in immune response against the B.1.1.529 strain for mRNA-1273.529 at Day 29 compared to the mRNA-1273.

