The number and percentage (rate) of participants achieving seroresponse at Day 29 will be summarized with 95% CI calculated using the Clopper-Pearson method for each group. The difference of SRR between mRNA-1273.529 and mRNA-1273 will be calculated with 95% CI based on stratified Miettinen-Nurminen method adjusted for age group. The non-inferiority in SRR of mRNA-1273.529 compared to mRNA-1273 will be considered demonstrated if the lower bound of the 95% of the SRR difference is $> -10\%$ based on the non-inferiority margin of 10%.

The primary immunogenicity objective (against the variant B.1.1.529) is considered met if non-inferiority is demonstrated based on GMR and SRR difference, specifically:

- If the lower bound of the 95% CI of the GMT ratio between mRNA1273.529 against the variant (B.1.1.529) at Day 29 as compared to 50 μ g mRNA1273 against B.1.1.529 at Day 29 is > 0.667 based on the non-inferiority margin of 1.5.

- The lower bound of the 95% CI of the SRR difference (50 µg mRNA-1273.529 against the variant B.1.1.529 at Day 29 - 50 µg mRNA-1273 against B.1.1.529) is > -10%.
- If non-inferiority is demonstrated, the lower bound of 95% CI of the GMT ratio will be compared to 1, if it's greater than 1, then superiority is demonstrated.

A supportive analysis for the primary immunogenicity endpoints may also be performed using Per-Protocol Immunogenicity Set. For immune response against the B.1.1.529 strain, in the ANCOVA model, antibody titers at Day 29 post-booster against the B.1.1.529 strain will be a dependent variable, and a group variable (mRNA-1273.529 and mRNA-1273) will be the fixed effect, adjusting for age groups (< 65, \geq 65 years), pre-booster SARS-CoV-2 status, and pre-booster titer if applicable; the model may also be adjusted for other characteristics. The difference of SRR between mRNA-1273.529 and mRNA-1273 will be calculated with 95% CI based on stratified Miettinen-Nurminen method adjusted for pre-booster SARS-CoV-2 status and age group.

Part F Cohort 2

Primary analysis set for immunogenicity objectives will be based on PPIS-Neg.

50 µg mRNA-1273.529 as the second booster dose will be compared to 50 µg mRNA-1273 as the second booster dose. For the primary objective on immune response for a second booster dose of 50 µg mRNA-1273.529, see [Section 4.2](#). The same analysis methods described for Part F Cohort 1 will be used for the primary immunogenicity objective for Part F Cohort 2.

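### SAP 4.3 gives about 89% global power for Part F Cohort 1 with 300 external comparators, but SAP 4.6 supplies about 150: about 73% (about 94% for non-inferiority alone)

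*SAP*

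**What the plan says.** SAP 4.3 (Part F, Cohort 1) takes 300 evaluable participants on 50 µg mRNA-1273.529 and 300 on the external 50 µg mRNA-1273 booster, pointing to Section 4.6 for the latter. On that basis "there is approximately 89% global power for the primary immunogenicity objectives with alpha level of 0.05 (2-sided"). It assumes a true GMR of 1.5 and that "the standard deviation of the log-transformed titer is 1.5, and the non-inferiority margin for GMR is 1.5"; the SRR is 90% in both groups with a 10% margin.

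SAP 4.6 gives the comparator's size: "A total of approximately 150 participants in the P201" 50 µg booster arm, primed with two 100 µg doses.

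Three other places determine what the power figure covers:

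- SAP 2.1 lists superiority among the Cohort 1 primary objectives: "To demonstrate superiority of the antibody response against the Omicron variant (B.1.1.529) of a first booster dose of mRNA-1273.529" over a first booster of mRNA-1273.
- SAP 4.2 sets a narrower success rule: "The primary immunogenicity objective is considered met if non-inferiority against B.1.1.529 (based on GMR and SRR difference) is demonstrated".
- SAP 6.4.3 tests superiority after non-inferiority: "If non-inferiority is demonstrated, the lower bound of 95% CI of the GMT ratio will be compared to 1". It specifies that the SRR difference "will be calculated with 95% CI based on stratified Miettinen-Nurminen method adjusted for age group".

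Protocol 8.3 carries the same 300 and 89%, and adds that the sponsor may use an external arm of fewer than 300 if the SAP records that decision before the Day 29 analysis.

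**The concern.** The power statement cites a section that gives half the comparator it assumes. Both are current text of SAP version 7.0, and no power is stated anywhere for 150 comparators.

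What is at stake is how the result is read. Someone relying on 89% would take a failed superiority test as fairly strong evidence against a true GMR of 1.5. If the comparator has 150 participants, such a failure is considerably more likely by chance alone. The probability of meeting the success rule also falls, though much less.

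**Working it through.** **Inputs.** From SAP 4.3: SD 1.5, true GMR 1.5, GMR margin 1.5, SRR 90% in both groups, SRR margin 10%, two-sided alpha 0.05. Group sizes are 300/300 (SAP 4.3) and 300/150 (SAP 4.6 for the comparator).

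**Log base.** The SAP does not state the log base of the SD. At 300/300, superiority power is 0.911 with natural log, 0.300 with log10 and 0.998 with log2. Only natural log leads to 89%, so it is used below.

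**GMR tests.** The standard error is 1.5 × √(1/n₁ + 1/n₂):

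- 300/300: 1.5 × √(2/300) = 0.1225
- 300/150: 1.5 × √(1/300 + 1/150) = 1.5 × √0.01 = 0.150

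With ln 1.5 = 0.4055, the true effect lies 0.4055 above the superiority boundary and 2 × 0.4055 = 0.811 above the non-inferiority boundary. In normal-approximation form, superiority power is:

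- 300/300: Φ(0.4055/0.1225 − 1.96) = 0.912 (noncentral t: 0.911)
- 300/150: Φ(0.4055/0.150 − 1.96) = 0.771 (noncentral t: 0.770)

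**SRR test.** Exact enumeration of the unstratified Miettinen-Nurminen test gives 0.979 at 300/300 and 0.943 at 300/150.

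**Combination,** multiplying the SRR and GMR tests as if independent:

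| | 300/300 | 300/150 |
|---|---|---|
| GMR non-inferiority | 1.000 | 0.9997 |
| SRR non-inferiority | 0.979 | 0.943 |
| GMR superiority | 0.911 | 0.770 |
| Non-inferiority on both (success rule) | 0.979 | 0.943 |
| Non-inferiority plus superiority | 0.979 × 0.911 = **0.892** | 0.943 × 0.770 = **0.726** |

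The stated 89% is therefore reproduced at 300/300 with superiority included. Non-inferiority alone gives 98%, so 89% is not a non-inferiority figure. The same reading fits the other power statements in SAP 4.3: Part G (stated 71%) comes to 70–71% with superiority and 82–83% without, and Part H (stated 60%) to 59–61% with and 67–69% without.

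**Sensitivity at 300/150:**

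- Any dependence between the SRR and GMR tests: from 0.9432 + 0.7695 − 1 = 0.713 up to 0.770.
- Unpooled normal approximation for SRR: 91.5% for non-inferiority and 70.6% with superiority (98.3% and 89.6% at 300/300).
- Age-stratified Miettinen-Nurminen, by simulation with 400,000 runs. If 20–40% are aged 65 or over in both groups (assumed), SRR power is 0.943–0.944. If the age mix differs, 20% against 40%, it is 0.931–0.933; at 10% against 50% it is 0.887.
- Adjustment for pre-booster titer, with residual SD 1.5 × √(1 − r²) and r assumed to be 0.3–0.5: power with superiority is 76.1–82.6%, against 91.5–94.8% at 300/300. The drop is still 12–15 points.
- Only 120–140 comparators evaluable (assumed): non-inferiority 0.922–0.937, and 0.650–0.703 with superiority.

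**The case against.** The best reply is that little turns on this. The protocol foresaw a smaller external arm, SAP 4.6 discloses it, and SAP 4.3 directs the reader there. The success rule is non-inferiority only, and its power with 150 comparators, about 94%, is above the 89% stated. The loss falls mainly on a superiority step that success does not require. The version 7.0 text comes late in the study, so correcting a sentence cannot alter enrolment, and the reported confidence interval for the GMR will show the precision achieved.

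Most of that is fair, and it limits the weight of the point. It does not make the 89% true. Superiority is a listed primary objective, and the 89% arises only when superiority is counted, so the like-for-like figure at 150 is about 73%. The allowance permits the smaller arm but does not supply its power.

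It is also fair that 73% depends on method. Natural log is inferred, independence is a simplification, and the ANCOVA adjusts for "pre-booster antibody titer level if applicable; the model may also be adjusted for other characteristics", which could recover some power. These are reasons to name the method and give a range. None of the 300/150 cases examined reaches 89%; the most favourable gives 82.6%.

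**Conclusion.** The concern holds. With the comparator that SAP 4.6 documents, global power for Part F Cohort 1 is about 73%, or 71.3–77.0% under any dependence between the tests. Power for the success rule is about 94%, down from about 98%, so the chance of missing it rises from about 2% to about 6%.

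These figures rest on SAP 4.3's assumptions, the natural-log scale, an unstratified Miettinen-Nurminen test, no covariate gain and all 150 comparators being evaluable. The last is uncertain, because SAP 5.5 admits only P201 participants in the Part B Per-Protocol Set, and SAP 4.6 does not say whether its 150 is counted after that restriction. The SAP should be corrected, but the validity of the analysis is not in question.

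**What to change.** In SAP 4.3, Part F Cohort 1:

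1. Replace the 300 external comparators with approximately 150, keeping the reference to Section 4.6.
2. Replace the 89% with approximately 94% power for non-inferiority (GMR and SRR difference) and approximately 73% global power for non-inferiority plus superiority. The sponsor's own recomputation with the planned stratified test would serve equally well. Either way, state the method, the log base and which tests the global figure includes.
3. Add that both figures are lower if fewer than 150 comparators are in the P201 Part B Per-Protocol Set.

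The 300 and 89% in Protocol 8.3 and the synopsis can stand as planning figures, since the allowance for a smaller arm follows them there.

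The cost is SAP wording only: no extra participants, and no change to tests, margins or decision rules.

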(mRNA-1273.214 second booster vs. 50 µg mRNA-1273 second booster) against the variant (B.1.1.529) is 1.5, the true GMR against ancestral SARS-CoV-2 is 1, the standard deviation of the log-transformed titer is 1.5, and the non-inferiority margin for GMR is 1.5, the true SRR against B.1.1.529 after mRNA-1273.214 as a second booster dose is 90% (same assumption for both 50 µg mRNA-1273.214 and 50 µg mRNA-1273), and non-inferiority margin for SRR difference is 10%.

With approximately 375 participants exposed to 50 µg mRNA-1273.214, there is at least 90% probability in this group to observe 1 participant reporting an AE if the true rate of AEs is 1%.

Part H

The target enrollment is approximately 500 participants for 50 µg mRNA-1273.222. Assuming 40% of participants will be excluded from the PP Set for Immunogenicity – SARS-CoV-2 negative (due to a SARS-CoV-2 infection prebooster), with approximately 300 participants in 50 µg mRNA-1273.222 and 260 participants in 50 µg mRNA-1273 (Part F, Cohort 2-50 µg mRNA-1273) in the PP Set for Immunogenicity and SARS-CoV-2 negative, there is approximately 60% power to demonstrate the primary immunogenicity objectives with an alpha of 0.05 (2-sided) at Day 29. The assumptions are: the true GMR (mRNA-1273.222 second booster vs. mRNA-1273 second booster) against Omicron BA.4/5 is 1.5, GMR (mRNA-1273.222 second booster vs. mRNA-1273 second booster) against ancestral SARS-CoV-2 D614G is 1, the standard deviation of the log-transformed titer is 1.5, and the non-inferiority margin for GMR is 1.5. The true SRR against Omicron BA.4/5 after mRNA-1273.222 as a second booster dose is 95% (same assumption for 50 µg mRNA-1273), and non-inferiority margin for SRR difference against Omicron BA.4/5 is 5%. The true SRR against ancestral SARS-CoV-2 D614G after mRNA-1273.222 as a second booster dose is 95% (same assumption for 50 µg mRNA-1273), and the non-inferiority margin for SRR difference against ancestral SARS-CoV-2 D614G is 10%.

With approximately 500 participants exposed to 50 µg mRNA-1273.222, there is at least 90% probability in this group to observe 1 participant reporting an AE if the true rate of AEs is 1%.

Part J

The sample size for Part J is not driven by statistical assumptions for formal hypothesis testing. The number of proposed participants is considered sufficient to provide a descriptive summary of the safety and immunogenicity of each treatment arm.

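### One control arm is sized at 300 for Part F Cohort 2 and Part G but at 260 for Part H, without explanation, and the stated 71% and 89% powers hold only at 300.

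*SAP*

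**What the plan says.** SAP 4.3 sizes three comparisons against the Part F Cohort 2 mRNA-1273 50 µg arm.

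- **Part F Cohort 2:** about 375 enrolled per arm, 20% excluded, about 300 evaluable in each arm, about 89% global power at two-sided 0.05.
- **Part G:** the exclusion assumption is "Assuming 20% of participants will be excluded from the PPIS-Neg", and the control count is "300 participants in 50 µg mRNA-1273 (Part F, Cohort 2-50 µg mRNA-1273) in the PPIS and SARS-CoV-2 negative". On alpha, "alpha of 0.025 (2-sided) will be allocated equally to each one of the two time points". The result is "there is approximately 71% global power to demonstrate the primary immunogenicity objectives with alpha of 0.025 (2-sided) at each time point".
- **Part H:** the control count is "260 participants in 50 μ g mRNA-1273 (Part F, Cohort 2-50 μ g mRNA-1273) in the PPIS and SARS-CoV-2 negative", with about 60% power at two-sided 0.05. The 40% exclusion quoted there takes the mRNA-1273.222 arm from 500 to 300. It does not produce the 260.

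Protocol 8.3 carries the same pair of counts, with 300 for Part F Cohort 2 and Part G and, for Part H, "mRNA-1273.222 and 260 participants in 50" µg mRNA-1273. So does the sample size text of the synopsis.

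**The concern.** The arm is named identically in the Part G and Part H paragraphs, and the analysis set is described in the same words, yet the count differs by 40. The two counts also come from different times. SAP 6.4.3 (Part H) says the Part F mRNA-1273 arm was enrolled in February 2022 and Part H in August 2022. Part H entered the protocol with Amendment 8 on 01 Aug 2022 (protocol 10.5.3), so the 260 was written after the control arm had been enrolled. The 300 is a planning figure: 375 less 20%.

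If 260 is also the right count for the B.1.1.529 comparisons, the current SAP and protocol still print powers for Part G and Part F Cohort 2 that rest on a superseded input. Part G is the formal hypothesis-testing comparison for mRNA-1273.214, and a reader of SAP 4.3 would take 71% as its power.

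**Working it through.** **Inputs (SAP 4.3; margins also in SAP 4.2).** True GMR 1.5 against B.1.1.529 and 1.0 against ancestral virus; SD of log titer 1.5; GMR margin 1.5; SRR 90% in both arms with a 10% margin. Alpha is two-sided 0.025 per time point for Part G (z = 2.2414) and two-sided 0.05 for Part F Cohort 2 (z = 1.9600). The SD is taken on the natural-log scale: on the log10 scale a single GMR component would have only 21% power.

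**Formulas.** With k = √(1/n₁ + 1/n₂):
- GMR superiority (true 1.5), or ancestral non-inferiority (true 1.0): Φ(ln 1.5 / (1.5k) − z), ln 1.5 = 0.4055.
- GMR non-inferiority against B.1.1.529 (true 1.5): Φ(2 ln 1.5 / (1.5k) − z), which is 1.000 to three decimals throughout.
- SRR non-inferiority: Φ(0.10 / (0.3k) − z), because √(0.9 × 0.1) = 0.3.
- Global power is the product of the components, treated as independent.

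**Reproducing the plan at 300/300.** k = 0.08165.
- Part G: GMR Φ(3.311 − 2.241) = 0.8575; SRR Φ(4.082 − 2.241) = 0.9672. Global 0.8575 × 0.8575 × 0.9672 = 0.711 (stated 71%).
- Part F Cohort 2: 0.9116 × 0.9831 = 0.896 (stated 89%).

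The 71% is reached only with superiority included. The three non-inferiority tests alone give 0.8575 × 0.9672 = 0.829.

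**At 300 test / 260 control.** k = 0.08473.
- Part G: GMR Φ(3.190 − 2.241) = 0.8286; SRR Φ(3.934 − 2.241) = 0.9547. Global 0.8286 × 0.8286 × 0.9547 = 0.656; non-inferiority only 0.8286 × 0.9547 = 0.791.
- Part F Cohort 2: 0.8907 × 0.9758 = 0.869.

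**At 260/260.** k = 0.08771.
- Part G: 0.7997 × 0.7997 × 0.9405 = 0.602; non-inferiority only 0.752.
- Part F Cohort 2: 0.8691 × 0.9672 = 0.841.

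| Test / control | Part G, all hypotheses | Part G, non-inferiority only | Part F Cohort 2 |
|---|---|---|---|
| 300 / 300 | 71.1% | 82.9% | 89.6% |
| 300 / 260 | 65.6% | 79.1% | 86.9% |
| 260 / 260 | 60.2% | 75.2% | 84.1% |

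Part G figures are per time point. With t distributions or a score variance for the SRR test, the 300/260 row becomes 64.6–65.6% for Part G (all hypotheses) and 86.4–86.9% for Part F Cohort 2.

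**Cross-check on Part H.** With SRR 95% and margins of 5% and 10%, 300/260 at two-sided 0.05 gives 0.8907 × 0.8907 × 0.7726 × 0.9997 = 0.613, against about 60% stated. At 300/300 it would be 66.7%. With the score variance the two values are 58.5% and 62.6%; 260 is the closer match either way. One method therefore reproduces all three stated powers from their own stated counts.

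**Exclusion rate.** 1 − 260/375 = 30.7%, but 375 is a target. If 325 had been dosed, 260 would be exactly a 20% exclusion.

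**The case against.** Four points can be made on the other side.

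1. **The counts are planning inputs from different dates.** An early assumption followed by a better-informed one is not an arithmetic error, and 71% and 89% do follow from their stated inputs. That stands. But both counts remain in current text, for one arm, with no note of which applies where.

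2. **260 may be a BA.4/5-specific count.** SAP 5.3 and 5.5 tie per-protocol membership to variant-specific titers: B.1.1.529 for Parts F and G, BA.4/5 for Part H. The Part H control count could therefore be the participants with BA.4/5 results. This is a real possibility. Neither document says so, Part H uses the same set wording as Part G, and SAP Table 3 lists only D614G and BA.1 for this arm. It can be neither confirmed nor excluded.

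3. **66% mixes a later control count with an early test-arm count.** That also stands. Nothing shows whether the mRNA-1273.214 arm reached 300, which is why the 260/260 row is given.

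4. **The objective is easier to meet than 71% or 66% suggests.** SAP 4.2 declares it met on the three non-inferiority tests at either Day 29 or Day 91. At 300/260 that is 79.1% on one day, and passing on either day is at least as likely.

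A reader might infer that both counts cannot be true, that Part G simply has 66% power, or that 31% of the control arm was excluded. The documents do not support these readings. Point 2 offers a way for both counts to hold, point 3 makes 66% conditional, and no actual dosed count is given.

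**Conclusion.** The unexplained difference is real and appears in SAP 4.3, protocol 8.3 and the synopsis. The stated 71% and 89% hold only with 300 controls. If 260 applies to the B.1.1.529 comparisons and the test arms still reach 300, they are about 66% and 87%, a loss of about 5 and 3 points. If the test arms also fall to 260, they are about 60% and 84%. The probability of meeting the Part G non-inferiority criteria at one time point moves from about 83% to 79% at 300/260.

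These figures rest on the plan's GMR, SD and SRR assumptions, a natural-log SD and independent components. The effect is confined to the planning statement: alpha, margins, models and success rules are untouched. It does not show that Part G's design lacks its stated power, because the documents leave open which count applies.

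**What to change.** Use one evaluable count for the Part F Cohort 2 mRNA-1273 50 µg arm in SAP 4.3, protocol 8.3 and the synopsis, or explain why it differs.

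- **If 260 applies to the B.1.1.529 comparisons:** restate Part G as about 66% per time point including superiority, and Part F Cohort 2 as about 87%, both conditional on 300 in the test arm. Base the control arm's exclusion rate on its actual dosed count; 31% is right only if 375 were dosed.
- **If 260 counts only participants with BA.4/5 titers:** say so in the Part H paragraph and keep 300 for Part F Cohort 2 and Part G.

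Either route changes wording only. No participants are added and no analysis changes; under the first route the stated powers become slightly less favourable.
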